5.4 Removal of Subjects from Therapy or Assessment

5.4.1 Discontinuation of Individual Subjects

A subject may withdraw from the study at any time. The Investigator may discontinue any subject's participation for any reason, including an AE, safety concerns or failure to comply with the protocol.

Subjects will be withdrawn from the study immediately if any one of the following occurs:

- Clinically significant abnormal laboratory result(s) or AE(s), as determined by the Investigator in consultation with the AbbVie SDP.
- The Investigator believes it is in the best interest of the subject.
- The subject requests withdrawal from the study.
- Inclusion and exclusion criteria violation was noted after the subject started study drug, when continuation of the study would place the subject at risk as determined by the AbbVie SDP (Section 5.2.1 and Section 5.2.2).
- Introduction of prohibited medications or dosages when continuation of the study drug would place the subject at risk as determined by the AbbVie SDP.
- The subject becomes pregnant while on study drug.
- Subject has dysplasia of the gastrointestinal tract or a malignancy, except for localized non-melanoma skin cancer. Discontinuation for carcinoma in-situ of the cervix is at the discretion of the Investigator.
- Subject is diagnosed with lupus-like syndrome, multiple sclerosis or demyelinating disease.

- Subject is significantly non-compliant with study procedures which would put the subject at risk for continued participation in the trial, as determined by the Investigator, in consultation with the AbbVie SDP.

If, during the course of study drug administration, the subject prematurely discontinues study drug use, the procedures outlined for the Premature Discontinuation Visit must be completed within 2 weeks of the last dose of study drug, and preferably prior to the initiation of another therapy. However, these procedures should not interfere with the initiation of any new treatments or therapeutic modalities that the Investigator feels are necessary to treat the subject's condition. Following discontinuation of the study drug, the subject will be treated in accordance with the Investigator's best clinical judgment.

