6.7 Toxicity Management

Subjects who develop a new infection while undergoing treatment with adalimumab should be monitored closely. Administration of study injections should be interrupted if a subject develops an infection requiring IV anti-infective treatment or if an infection meets the definition of "serious" (see Section 6.1 for definitions). Study drug may be restarted once the physician determines that the infection has been successfully treated. Otherwise prohibited concomitant medications may be given if medically necessary. Prior to use,

every attempt should be made to contact the AbbVie Study Physician for direction on re-introduction of adalimumab therapy after prohibited medication administration.

If the subject must undergo elective surgery, the study injections must be interrupted two weeks prior to the surgery. If the subject must undergo emergency surgery, the study injections must be interrupted at the time of the surgery. The injectable study drug can recommence at least two weeks after surgery once the physician has examined the surgical site and determined that it has healed and there is no sign of infection.

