the study visit for that window. If two visits are equidistant from the target day, then the later visit will be used for reporting.

The visit windows and the nominal (target) day for each study visit are shown in the following tables.

Table 3. Visit Windows for Analysis of Efficacy Variables (Except IBDQ, EQ-5D, WPAI, and SES-CD), Laboratory Parameters, and Vital Signs

| Protocol Specified Visit | | | |
|---------------------------------|--------------------|--------------------|--------------------|
| Week | Lower Bound | Nominal Day | Upper Bound |
| 0 | -999 | 1 | 1 |
| 8 | 2 | 57 | 85 |
| 16 | 86 | 113 | 141 |
| 24 | 142 | 169 | 197 |
| 32 | 198 | 225 | 253 |
| 40 | 254 | 281 | 309 |

Table 4. Visit Windows for Analysis of IBDQ, EQ-5D, WPAI, and Abdominal Pain Rating Scale

| Protocol Specified Visit | | | |
|---------------------------------|--------------------|--------------------|--------------------|
| Week | Lower Bound | Nominal Day | Upper Bound |
| 0 | -999 | 1 | 1 |
| 16 | 2 | 113 | 169 |
| 32 | 170 | 225 | 253 |
| 40 | 254 | 281 | 309 |

Table 5. Visit Windows for SES-CD

| Protocol Specified Visit | | | |
|---------------------------------|--------------------|--------------------|--------------------|
| Week | Lower Bound | Nominal Day | Upper Bound |
| 0 | -999 | 1 | 1 |
| 40 | 2 | 281 | 561 |

Note: If an endoscopy was done within 7 days after first dose of Study M14-347, the SES-CD will still be used as Study M14-347 Baseline value.

CD-Related Concomitant Therapy

Subjects in whom systemic corticosteroids that were not being taken at Baseline of Study M14-347 and are initiated during the study or who have dosages of corticosteroids increased to greater than the dose taken at Baseline of Study M14-115 will be censored for efficacy assessments (i.e., will be considered non-responders for categorical endpoints and will have Study M14-115 Baseline values carried forward for non-categorical assessments) from that point through the end of the study. These subjects will continue to be evaluated in the safety population.

The equivalent steroid dose will be determined based on the table below:

| Corticosteroid | Equivalent Dose (mg) |
|--------------------|----------------------|
| Cortisone | 25 |
| Hydrocortisone | 20 |
| Prednisone | 5 |
| Prednisolone | 5 |
| Triamcinolone | 4.0 |
| Methylprednisolone | 4.0 |
| Betamethasone | 0.75 |
| Dexamethasone | 0.75 |
| Budesonide | 1 |
| Beclomethasone | 5 |
| Beclometasone | 5 |

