If a subject met the censoring criteria for CD related concomitant therapy during Study M14-115, all binary efficacy endpoints will be No in Study M14-347, all observed values in Study M14-347 will be replaced by Study M14-115 Baseline values.

Dose Escalation

Subjects who had dose escalated to 40 mg ew will be censored for efficacy assessments (i.e., will be considered non-responders for categorical endpoints and will have

Study M14-115 Baseline values carried forward for non-categorical assessments) from that point through the end of the study.

Definition of Missing Data Imputation

Missing data imputation will be done only for efficacy variables (categorical and continuous variables). For the analysis other than efficacy, no imputation will be done for missing values.

Non-Responder Imputation (NRI)

The NRI approach is used for binary efficacy data. These variables can take values of 'Achieved' or 'Not Achieved' or may be missing for any reason including discontinuation from study. According to the NRI imputation approach, all missing values will be considered as 'Not Achieved.'

Observed Case (OC)

Observed case analysis will be performed such that missing values will not be imputed. However, all observed values will be replaced by Study M14-115 Baseline value once subjects met the censoring criteria for CD-related concomitant therapy or dose escalation, whichever is earlier.

Last Observation Carried Forward (LOCF)

For all variables (categorical variables and continuous variables), the following rules will be used for the LOCF approach:

1. Baseline and Pre-Baseline values will not be used to impute the missing Post-Baseline values.
2. Missing values after Study Day 1 will be imputed using the latest non-missing values after Day 1 and prior to the missing value. If there are no non-missing values after Baseline, then the LOCF value will be missing.

Rule for CDAI Calculation

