- Change in European Quality of Life 5 Dimensions (EQ-5D) from Study M14-115 Baseline over time.
- Change in CDAI from Study M14-115 Baseline over time.
- Change in SFPS from Study M14-115 Baseline over time.
- Change in Abdominal Pain Rating Scale score from Study M14-115 Baseline over time.
- Change in each CDAI component subscore (number of liquid or very soft stools, abdominal pain rating, general well-being, CD related complications, anti-diarrhea use, abdominal mass, hematocrit, body weight) from Study M14-115 Baseline over time.
- Time to first dose escalation.

- Proportion of subjects who require weekly dosing at Week 1 of Study M14-347.
- Proportion of subjects with major CD related event (e.g., hospitalization, bowel surgery, abscess drainage).
- Proportion of subjects with CD related hospitalization.
- Proportion of subjects with CD related surgery.
- Proportion of subjects requiring dose escalation to weekly dosing during this study.
- Proportion of subjects with no draining fistulas over time among subjects with draining fistula at Study M14-115 Baseline.
- Proportion of subjects in each treatment group with > 50% reduction from Baseline of Study M14-115 in the number of draining fistulas over time among subjects with draining fistula at Study M14-115 Baseline.
- Resolution of extraintestinal manifestations over time.
- Proportion of subjects who achieve symptomatic remission, defined as average daily stool frequency ≤ 1.5 (and not worse than Study M14-115 Baseline) and average daily abdominal pain ≤ 1.0 (and not worse than Study M14-115 Baseline) over time among subjects with Study M14-115 Baseline average daily stool frequency ≥ 2.5 or average daily abdominal pain ≥ 2.0 .
- Proportion of subjects who achieve symptomatic remission, defined as average daily stool frequency ≤ 2.8 (and not worse than Study M14-115 Baseline) and average daily abdominal pain ≤ 1.0 (and not worse than Study M14-115 Baseline) over time among subjects with Study M14-115 Baseline average daily stool frequency ≥ 4.0 or average daily abdominal pain ≥ 2.0 .
- Proportion of subjects who achieve symptomatic response, defined as average daily stool frequency at least 30% reduction from Study M14-115 Baseline and average daily abdominal pain not worse than Study M14-115 Baseline or average daily abdominal pain at least 30% reduction from Study M14-115 Baseline and average daily stool frequency not worse than Study M14-115 Baseline, over time.

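### SAP 6.0 counts steroids and weekly dosing as failure but not a prohibited non-steroid Crohn's therapy or Crohn's bowel surgery, so a subject with either can be scored as a maintained responder

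*SAP*

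**What the plan says.** The primary variable (SAP 10.2) is the proportion with endoscopic improvement at Week 40 among those with endoscopic improvement at Week 0. It is reported with a two-sided 95% confidence interval and with NRI for a missing Week 40 SES-CD. SAP 6.0 gives three routes to non-response that do not depend on the score itself:

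- **Corticosteroids.** The rule reads "Subjects in whom systemic corticosteroids that were not being taken at Baseline of Study M14-347 and are initiated during the study", and then adds doses raised above the M14-115 Baseline dose. It carries over for subjects who met it during M14-115.
- **Escalation.** "Subjects who had dose escalated to 40 mg ew will be censored for efficacy assessments" from that point to the end of the study.
- **Missing data.** "According to the NRI imputation approach, all missing values will be considered as" not achieved.

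The Observed Case convention names the same two events and no others: "all observed values will be replaced by Study M14-115 Baseline value once subjects met the censoring criteria for CD-related concomitant therapy or dose escalation".

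Protocol 5.2.3.3 prohibits other biologics, tofacitinib, cyclosporine, tacrolimus and mycophenolate, among others. On what follows if one is used, protocol 5.4.1 lists as a reason for withdrawal "Introduction of prohibited medications or dosages when continuation of the study drug would place the subject at risk", as judged by the study designated physician. Protocol 6.7 states "Otherwise prohibited concomitant medications may be given if medically necessary" and, on operations, "The injectable study drug can recommence at least two weeks after surgery once the physician has examined the surgical site" and found it healed. SAP 10.3 reports "Proportion of subjects with CD related surgery" as an endpoint of its own.

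**The concern.** The study has one arm, no comparator and no tests (SAP 10.1), so the maintenance proportion and its interval are the whole primary result. A success reached on another biologic, or after bowel surgery, would be credited to adalimumab maintenance, and no control arm carries the same error. The SAP already takes a composite-failure approach: a steroid start, or more of the study drug itself, makes the subject a failure whatever the endoscopy shows. It gives no reason why changing to another drug class or having bowel surgery should be treated differently.

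**Working it through.** The plan has no figure to reproduce: SAP 4.3 reports no sample-size calculation, and no rescue or surgery rate is assumed anywhere. The check is a rule trace, followed by an illustration of size.

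**1. Which events lead to non-response?**

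| Event after Week 0 | Rule | Result |
|---|---|---|
| New systemic steroid, or dose above M14-115 Baseline dose | SAP 6.0, CD-Related Concomitant Therapy | Non-responder |
| Escalation to 40 mg ew | SAP 6.0, Dose Escalation; protocol 8.1.4.1 | Non-responder |
| No Week 40 SES-CD | SAP 6.0 and 10.2, NRI | Non-responder |
| Prohibited non-steroid Crohn's therapy | None | Observed value used |
| Crohn's-related bowel surgery | None; separate endpoint in SAP 10.3 | Observed value used |

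Prohibited intravenous steroids fall in the first row when newly started or above the M14-115 Baseline dose. The gap therefore concerns non-steroid therapy and surgery.

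**2. Does the protocol remove such subjects?** Not always. Withdrawal under 5.4.1 depends on a judgement that continuing study drug would place the subject at risk. Section 6.7 allows prohibited drugs in some circumstances, discusses re-introducing adalimumab afterwards, and lets study drug restart after surgery. The need for alternative or prohibited therapy is listed in SAP 8.0 as a reason for stopping study drug, but that is a disposition category and not an efficacy rule.

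**3. Trace of one subject who stays.** The subject is improved at Week 0, so is in the denominator. The dose stays at 40 mg eow and no steroid is started, so neither override applies. Another biologic is given, or bowel surgery is done, and no rule responds. The Week 40 endoscopy is read centrally, so the value is observed and neither NRI nor the LOCF sensitivity analysis acts on it. If the score meets the SAP definition (SES-CD at most 4, at least 2 points below M14-115 Baseline, no individual variable above 1), the subject is scored as achieved.

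**4. Subjects who leave.** A premature-discontinuation endoscopy is done when discontinuation falls after Week 24 (protocol 5.1), and SAP Table 5 assigns any SES-CD from Day 2 to Day 561 to Week 40. Protocol 5.4.1 wants these procedures within two weeks of the last dose and only preferably before another therapy. An endoscopy after the new therapy or the operation is therefore possible, and it would count as an observed Week 40 value.

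**5. Size (illustration).** Enrolled N = 252 (SAP 4.2). The number of Week 0 improvers is not given; assume 20% to 50%. One subject moved from responder to non-responder changes the proportion by 100/n points.

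| Assumed share | n | 100/n (points) |
|---|---|---|
| 20% | 50 | 2.0 |
| 30% | 76 | 1.3 |
| 40% | 101 | 1.0 |
| 50% | 126 | 0.8 |

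For n = 76 and an assumed 38 responders, with exact (Clopper-Pearson) intervals because the SAP names no method:

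| Assumed cases k | (38 − k)/76 | 95% CI |
|---|---|---|
| 0 | 50.0% | 38.3 to 61.7 |
| 2 | 47.4% | 35.8 to 59.2 |
| 4 | 44.7% | 33.3 to 56.6 |

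The values of k are hypothetical.

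**The case against.** The strongest reply is that the main path of worsening disease is already covered. Inadequate response leads to weekly dosing or steroids, both of which are failures, and subjects who leave without an endoscopy fail under NRI. To be miscounted, a subject must avoid both events, receive a non-steroid therapy or an operation, have a Week 40 value and still meet the definition. Week 0 improvers may seldom need that within 40 weeks. The SAP also matches the protocol's own steroid and escalation rules, and using observed values after other events can be defended in a descriptive study. All of this bears on how often the gap matters, and it stands. It does not close the gap: the SAP neither states nor justifies a treatment-policy approach, and its two existing rules point the other way.

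A reader might go further than the documents allow in four ways:

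- **That every rescued or operated subject inflates the rate.** One who misses the Week 40 definition is already a non-responder.
- **That resection itself lowers the score, because missing SES-CD variables are set to 0 when 8 or fewer are missing.** This depends on how a resected segment is recorded, and the scoring appendices cannot be read in the public copy. It is a conditional risk only.
- **That protocol 6.7 plans for Crohn's rescue.** Its medication sentence sits in a paragraph on infections, and its surgery paragraph covers any operation. The section shows that staying in the study is possible, no more.
- **That immunosuppressant increases or rectal therapy plainly belong in the primary failure rule.** Both are already barred (protocol 5.1, 5.2.3.2, 5.2.3.3), and nothing in the documents ranks them above a steroid start.

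**Conclusion.** The point holds as a gap in the SAP's handling of intercurrent events. Applied as written, the rules score as maintained a Week 0 improver who received a prohibited non-steroid Crohn's therapy or had Crohn's bowel surgery, provided the Week 40 SES-CD is observed and qualifies. The same gap affects the other binary endpoints. The bias can only be upward, and it comes only from subjects who meet the definition. The documents give no number of cases, so the effect may be zero. Each case would be worth about 0.8 to 2.0 percentage points on the primary proportion, on the assumption of 126 down to 50 Week 0 improvers. The plan should be changed, but nothing here shows that the primary rate is materially inflated.

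**What to change.** Extend the failure rule in SAP 6.0. From first use of a prohibited non-steroid systemic Crohn's therapy, or from adjudicated Crohn's-related bowel surgery, the subject is a non-responder for binary efficacy endpoints through the end of the study. Tabulate the number of subjects meeting each failure rule, including zero counts. Treat an immunosuppressant start or increase, and rectal therapy, as failure in a sensitivity analysis. State how resected segments are recorded and, if they are recorded as missing, exclude them from the rule that sets missing SES-CD variables to 0.

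The cost is some SAP wording and a derived flag. Medication dates and doses are already collected (protocol 5.2.3.1), and major Crohn's events, of which surgery is a component, are adjudicated (SAP 6.0, 12.1). One detail needs care: SAP 7.3 leaves drugs started after the last dose of study drug out of its concomitant category, so the flag should use the recorded start dates up to the endoscopy. The downside is a slightly lower reported response rate if any cases exist. Treatment of subjects does not change.

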The EQ-5D consists of 2 pages. The first page measures 5 dimensions of the health status (mobility, self-care, usual activities, pain/discomfort, and anxiety/depression) with 5 levels per dimension (no problems, slight problems, moderate problems, severe problems, and unable corresponding to Level 1 to Level 5 respectively). The second page is an EQ Visual Analogue Scale (EQ VAS). EQ-5D health states, defined by the EQ-5D-5L descriptive system on the first page, may be converted into a single index value. The change from baseline of the index value and EQ VAS will be analyzed and reported. UK scoring algorithm will be used (Table 7).

Table 6. An EQ-5D-5L Value Set for England

| | Central Estimate | Value for Health State 23245 |
|--|------------------|---|
| Mobility | | |
| No Problem | 0 | |
| Slight | 0.051 | 0.051 |
| Moderate | 0.063 | |
| Severe | 0.212 | |
| Unable | 0.275 | |
| Self-Care | | |
| No Problem | 0 | |
| Slight | 0.057 | |
| Moderate | 0.076 | 0.076 |
| Severe | 0.181 | |
| Unable | 0.217 | |
| Usual Activities | | |
| No Problem | 0 | |
| Slight | 0.051 | 0.051 |
| Moderate | 0.067 | |
| Severe | 0.174 | |
| Unable | 0.190 | |
| Pain/Discomfort | | |
| No | 0 | |
| Slight | 0.060 | |
| Moderate | 0.075 | |
| Severe | 0.276 | 0.276 |
| Unable | 0.341 | |
| Anxiety/Depression | | |
| Not | 0 | |
| Slight | 0.079 | |
| Moderate | 0.104 | |
| Severe | 0.296 | |
| Unable | 0.301 | 0.301 |
| The value for health state 23245: 1 – 0.9675 × (sum of the subscores) | | 1 – 0.9675 × (0.051 + 0.076 + 0.051 + 0.276 + 0.301) = 0.270 |

The index value is $1 - 0.9675 \times \text{sum of 5 components based on central estimates.}$

The minimum index value is – 0.281 (health state 55555), and the maximum index value is 1 (health state 11111). (Reference: Devlin N, Shah KK, Feng Y, et al. Valuing health-related quality of life: an EQ-5D-5L value set for England. Health Econ. 2017.).

If one of the 5 dimensions is missing, the EQ-5D index value will be missing.

CD Related Hospitalizations and Major CD Related Events

CD related hospitalizations and major CD related events will be adjudicated according to the hospitalization adjudication charter.

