10.3 Additional Efficacy Analyses

For additional efficacy endpoints, the baseline is defined as the Baseline in Study M14-115. The additional efficacy variables are listed as below.

- Proportion of subjects with CDAI remission (CDAI < 150) over time among subjects with CDAI remission at Week 0 of Study M14-347.
- Proportion of subjects with endoscopic improvement, defined as an SES-CD ≤ 4 and at least 2 point reduction versus Study M14-115 Baseline and no subscore greater than 1 in any individual variable at Week 40.
- Proportion of subjects with CDAI remission (CDAI < 150) over time.
- Proportion of subjects with CDAI < 150 at Week 40 and SES-CD ≤ 4 and at least a 2 point reduction versus Study M14-115 Baseline and no subscore greater than 1 in any individual variable at Week 40 among subjects with CDAI < 150 at Week 0 and SES-CD ≤ 4 and at least a 2 point reduction versus Study M14-115 Baseline and no subscore greater than 1 in any individual variable at Week 0 of Study M14-347.
- Proportion of subjects with CDAI < 150 at Week 40 and SES-CD ≤ 4 and at least a 2 point reduction versus Study M14-115 Baseline and no subscore greater than 1 in any individual variable at Week 40.
- Proportion of subjects with endoscopic response at Week 40 among subjects with endoscopic response at Week 0 of Study M14-347.
- Proportion of subjects with endoscopic response at Week 40.
- Change from Study M14-115 Baseline in fecal calprotectin level over time.

- Proportion of subjects with hs-CRP < 5 mg/L and fecal calprotectin < 250 µg/g over time among subjects with hs-CRP < 5 mg/L and fecal calprotectin < 250 µg/g at Week 0 of Study M14-347.
- Proportion of subjects with hs-CRP < 5 mg/L and fecal calprotectin < 250 µg/g over time.
- Proportion of subjects with CDAI < 150, hs-CRP < 5 mg/L, and fecal calprotectin < 250 µg/g over time among subjects with CDAI < 150, hs-CRP < 5 mg/L, and fecal calprotectin < 250 µg/g at Week 0 of Study M14-347.
- Proportion of subjects with CDAI < 150, hs-CRP < 5 mg/L, and fecal calprotectin < 250 µg/g over time.

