12.0 Summary of Changes

12.1 Summary of Changes Between the Latest Version of Protocol and the Current SAP

The following efficacy variables are mentioned in the protocol but will not be summarized as they were removed from Study M14-115 protocol:

Proportion of subjects with predicted endoscopic improvement at Week 40, using the 3 definitions and equations.

Correlation between actual SES-CD and Predicted SES-CD:

In addition, change in Bristol Stool Scale score from Baseline over time will not be summarized as Bristol Stool Chart data in ePRO was not collected in Study M14-347.

The following efficacy variables are not mentioned in the protocol but are added to the SAP:

Proportion of subjects with CD related hospitalization: CD related hospitalization is a component of major CD related event.

Proportion of subjects with CD related surgery: CD related surgery is a component of major CD related event.

The following efficacy endpoints are added because they are used in new CD studies.

Proportion of subjects who achieve symptomatic remission, defined as average daily stool frequency ≤ 2.8 (and not worse than Study M14-115 Baseline) and average daily abdominal pain ≤ 1.0 (and not worse than Study M14-115 Baseline) over time among subjects with Study M14-115 Baseline average daily stool frequency ≥ 4.0 or average daily abdominal pain ≥ 2.0 : This endpoint is used for new CD studies as a primary efficacy endpoint.

Proportion of subjects with a decrease in SES-CD $> 50\%$ from Study M14-115 Baseline (or for subjects with an SES-CD of 4 at Study M14-115 Baseline, at least a 2-point reduction from Study M14-115 Baseline) at Week 40.

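### Read literally, SAP 6.0's blanket 'No' for subjects censored in M14-115 turns recorded CD events and dose escalations into non-events; separately, its observed-case analysis does not use continuous efficacy values seen after escalation

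*SAP*

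**What the plan says.** **The 'No' rule.** SAP 6.0 (CD-Related Concomitant Therapy) covers subjects who had already met the censoring criteria in the parent study. For them "all binary efficacy endpoints will be No in Study M14-347", and their observed M14-347 values are overwritten with M14-115 Baseline. No endpoint is excepted. The M14-115 criteria are not in these documents; the only criteria given under that heading concern systemic corticosteroids.

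**The endpoints it reaches.** SAP 10.3 introduces its list with "The additional efficacy variables are listed as below". The list includes:

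- "Proportion of subjects with major CD related event (e.g., hospitalization, bowel surgery, abscess drainage"
- "Proportion of subjects with CD related hospitalization", with a matching item for surgery
- "Proportion of subjects who require weekly dosing at Week 1 of Study M14-347"
- "Proportion of subjects requiring dose escalation to weekly dosing during this study"

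SAP 12.1 presents hospitalization and surgery as added efficacy variables, giving as its reason for the first that "CD related hospitalization is a component of major CD related event". On how events are established, SAP 6.0 says "CD related hospitalizations and major CD related events will be adjudicated according to the hospitalization adjudication charter".

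**Dose escalation and continuous endpoints.** SAP 6.0 (Dose Escalation) censors escalated subjects for efficacy from escalation to study end: non-responder for categorical endpoints, M14-115 Baseline for the rest. The Observed Case paragraph leaves missing values missing but repeats this substitution. SAP 10.3 plans LOCF and observed-case summaries for continuous endpoints. The protocol states Baseline carry-forward only in its corticosteroid rule (5.2.3.2). It states NRI after escalation only for the primary endpoint (8.1.4.1) and the categorical endpoints (8.1.4.2).

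**The concern.** A rule that imputes failure should push every endpoint in the unfavourable direction. Setting a binary variable to 'No' does that for remission or response. It does the opposite when the variable records a hospitalization, an operation or a move to weekly dosing. SAP 3.0 says that its conventions guide the programming, so a programmer who follows the sentence would overwrite recorded or adjudicated events. The error can only lower the reported event and escalation proportions.

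The observed-case issue is one of labelling and information. A reader expects an observed-case table to show what was observed. Here, visits after escalation carry a substituted value, although escalation is a planned path in a study of long-term efficacy. The protocol does not state this substitution for continuous endpoints.

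**Working it through.** The documents contain no figure to reproduce: SAP 4.3 reports no sample size calculation and SAP 10.1 plans no tests. The check is a comparison of the text, followed by arithmetic for scale.

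**Part (a): the text**

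| Efficacy variable (SAP 10.3) | Meaning of 'No' | Exempted in SAP 6.0? |
|---|---|---|
| CDAI remission, endoscopic improvement and similar | Unfavourable | Not needed |
| Major CD-related event | No event | No |
| CD-related hospitalization | No event | No |
| CD-related surgery | No event | No |
| Weekly dosing at Week 1 | Not on weekly dosing | No |
| Dose escalation during study | Not escalated | No |

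Time to first dose escalation is not binary, and SAP 10.3 gives it its own censoring rule: subjects without the event are censored at the last dose date. A subject censored in M14-115 who escalates is therefore an event in that analysis and a 'No' in the escalation proportion. The two counts differ by exactly the number of such subjects.

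**Part (a): scale.** SAP 4.2 gives 252 enrolled; I assume all were dosed. Suppressing s events lowers a proportion by s/252:

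- s = 1: 1/252 = 0.40 percentage points
- s = 3: 1.19
- s = 5: 1.98
- s = 10: 3.97

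If c subjects were censored in M14-115 and the true event rate were 10% in everyone (both assumed), the reported rate is 0.10 × (252 − c)/252. For c = 5, 13, 25 and 50 this gives 9.8%, 9.5%, 9.0% and 8.0%.

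**Part (b): formula.** Consider one post-baseline visit and set steroid-censored subjects aside. Let e be the share of observed values from already escalated subjects, D those subjects' actual mean change from M14-115 Baseline, and M the mean change in the others.

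- Actual mean = (1 − e)M + eD
- SAP observed-case mean = (1 − e)M + e × 0
- Reported minus actual = −eD, whatever M is

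**Part (b): scale for CDAI.** The 70-point response threshold is from SAP 6.0; e and the range of D are assumptions. A positive shift moves an average improvement toward zero; a negative one flatters it.

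| e | D = −70 | D = 0 | D = +25 |
|---|---|---|---|
| 0.05 | +3.5 | 0 | −1.25 |
| 0.10 | +7.0 | 0 | −2.5 |
| 0.20 | +14.0 | 0 | −5.0 |

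One escalated subject at −70 among 252 observed values (the maximum) shifts the mean by 70/252 = 0.28 points.

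**The case against.** **On (a).** The SAP's intent is not hard to guess. The same section calls censored subjects non-responders, describes binary efficacy data under NRI as achieved or not achieved, and uses 'No' as the bad result for steroid discontinuation. Nobody achieves a hospitalization. CD events also have their own adjudication paragraph. The affected group may be empty, because exclusion 8 (Protocol 5.2.2) removes subjects who did not comply with M14-115 medication requirements. Hospital admissions remain in the serious adverse event tables (SAP 11.2.2.4), and escalations remain in the time-to-event analysis.

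All of this stands as evidence of intent and as a limit on the effect. None of it is an exemption. The adjudication paragraph says how events are classified, not that they escape the rule. The serious adverse event tables are not described as using the adjudicated CD-related classification, so they do not replace the event proportions.

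**On (b).** Treating escalation as failure is a legitimate choice. The SAP defines its observed-case rule openly, and the protocol leaves detail to the SAP (8.1). SAP 12.1 lists dropped and added variables rather than handling conventions, so the rule's absence there conceals nothing. These points stand. What remains is an inaccurate label and a useful summary that is missing.

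**Stronger readings that the documents do not support.**

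- A reader might infer that no planned table shows any continuous outcome after escalation. The substitution covers efficacy assessments only; laboratory values and vital signs are summarized by visit in SAP 11.3 and 11.4.
- A reader might take LOCF replacement as settled. The general Dose Escalation paragraph appears to reach LOCF, but the LOCF paragraph does not say so. Its bar on Baseline values concerns filling missing data only.
- A reader might think that an escalated subject contributes 0 at every visit. Replacement starts at escalation; earlier visits keep their values.

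**Conclusion.** Part (a) holds: the rule is wrong as written, with limited effect. Its literal application reports recorded CD events, weekly dosing and escalations as absent in subjects censored during M14-115, and lets two escalation analyses disagree. The total size cannot be computed, because the documents give neither the number censored nor the event counts; the number affected may be zero. The 0.40 percentage points per suppressed event assumes that all 252 enrolled subjects were dosed. For the primary endpoint 'No' is the unfavourable result, so this mechanism does not flatter it.

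Part (b) holds as a cheap improvement. From escalation onward, the observed-case change from M14-115 Baseline is 0 by construction for continuous efficacy endpoints. No direction of bias is shown: under the assumed values, the shift in mean CDAI change runs from 14 points toward zero to 5 points in the flattering direction, and is 0 if escalated subjects are on average back at Baseline.

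**What to change.** 1. State in SAP 6.0 that the 'No' and non-responder rules apply only to response- and remission-type endpoints, including steroid discontinuation. Count major CD-related events, CD-related hospitalization, CD-related surgery, weekly dosing at Week 1 and dose escalation as recorded or adjudicated, regardless of censoring.
2. Keep the Baseline-substituted analysis under a label that says what it is. Add one observed-case summary of the continuous efficacy endpoints using values actually observed after escalation, with the protocol's corticosteroid rule still applied. Say whether the substitution also applies to LOCF.
3. Optionally, note the escalation carry-forward in SAP 12.1 for tidiness.

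The cost is a scope sentence, a relabelling and one extra set of descriptive tables. Reported event and escalation proportions may be slightly higher. No planned analysis is lost.
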